Comparative Analysis of Zero Echo-time MRI and CT for Pediatric Craniosynostosis

NCT#04704284

23May2022

Title of the Study: Comparative analysis of zero echo-time MRI and CT for pediatric craniosynostosis. Ver 3 May 23, 2022.

Principle Investigator: [name] Neuroradiology

Abstract

Zero echo-time (ZTE) MRI (K132376) is an emerging technique that has been shown to adequately image bone and will likely allow eventual widespread imaging of osseous structures. The opportunity to exchange standard CT evaluation for a radiation-free modality is desirable, particularly in the pediatric population. A promising clinical application is the use of ZTE for diagnosing craniosynostosis, potentially precluding the use of the standard volumetric head CT scan. We propose a comparative analysis between zero echo-time MRI and CT to assess their effectiveness in diagnosing this entity. Our hypothesis is that ZTE is concordant with CT for suture visualization and imaging diagnosis, permitting its use in the clinical setting for this purpose.

Research Plan

1. Specific Aims

To establish whether ZTE imaging of the infant calvarium can provide equivalent information to CT and allow for a reliable diagnosis of craniosynostosis in a child. This aim is based on the hypothesis that there will be 90% or greater concordance between ZTE and CT findings.

2. Background & Significance

Magnetic resonance imaging (MRI) has become the primary workhorse for pediatric neuroradiology, providing superior imaging of soft tissues in the brain, head, neck and spine, while offering the added benefit of having no ionizing radiation. Evaluating cortical bone, however, continues to be a limitation with conventional MRI sequences. The contents within cortical bone (inorganic minerals, collagen matrix and various water concentrations) and their tightly organized structure result in very short T2 values ($T2 \sim 300-400 \,\mu s$) and rapid magnetization decay which yield signal voids and insufficient image contrast.

Computed tomography (CT), therefore, continues to be the primary modality for evaluating osseous structures. This modality is not ideal in children who have increased sensitivity to the adverse effects of radiation. Developing a comparable MR sequence which can evaluate bone without radiation is critical and aligns with the ALARA ("as low as reasonably achievable") radiation safety principle to minimize radiation doses in children.

Three dimensional proton density-weighted zero echo-time (ZTE) is a developing technique that uses proton density differences rather than T2 relaxation time differences to achieve contrast. It has been used to better image bone structure within the calvarium, spine and

extremities¹⁻⁵ and has been explored for use in attenuation correction for PET/MR studies⁶⁻⁸. The sequence is performed without preparation pulses or multiple echoes, rendering it time-efficient and (if performed alone), usually precluding the need for sedation¹. Alternatively, it can easily be added to a more complete MR exam, providing an efficient "one stop" evaluation.

The diagnostic utility of ZTE is not yet established and a comparative validation study of ZTE with CT is needed before reliably using this in the clinical setting for preoperative purposes. If ZTE is shown to be non-inferior to CT for evaluation of craniosynostosis, clinical practice will be substantially improved; neurosurgeons as well as parents and children may be offered a radiation free imaging tool. This is particularly advantageous for this population of children which may require multiple follow-up exams after surgical correction. Moreover, this could serve as an initial study preceding evaluation of other osseous structures including facial bones and skull base. The findings in this study could also drive further technological advancements to include the creation of surface renderings based on ZTE data for anatomic modeling.

3. Study Design

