3.3 MRI and CT evaluation

Four CAQ certified neuroradiologists will independently evaluate CT and ZTE images in separate sessions. There will be at least a two-week time window between readings of CT and ZTE to diminish recall bias. ZTE data will be presented in three display formats: (1) raw magnitude image with multiplanar reformats, (2) bright-bone reconstructions, (3) 3D volume renderings. CT data will be presented in two display formats: (1) source images with multiplanar reformats and (2) 3D volume renderings. The images will be reviewed in a blinded fashion during separate interpretation sessions to prevent recall bias.

3.4 Data Collection:

Each observer will provide ordinal ratings with regard to (a) visibility of each major cranial suture and fontanelles [1 = poorly seen, 2 = partially seen, 3 = fully seen] and (b) confirmation of diagnosis based on the clinical question [+1 = pathologic abnormality present, 0 = unable to tell, -1 = pathologic abnormality absent].

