3.5 Data Analysis

Sample size estimation for this interobserver agreement study was based on a confidence interval approach⁹. Using 4 raters and 3 levels of rating for their assessment, with type I error (alpha) fixed at 0.05 and an expected 80/20 probability of the absence or presence of craniosynostosis, respectively, we will have 80% power to claim the interobserver kappa statistics is greater than 0.7 when the true kappa is 0.95 with a sample size of 37

patients. Interobserver agreement will be summarized by the kappa coefficient statistic and corresponding 95% confidence intervals.

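### Section 3.5 names no signed ZTE-versus-CT comparison of suture visibility: interobserver kappa measures reader consistency, and concordance ignores which modality is better

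*Combined protocol and SAP*

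**What the plan says.** - **Hypothesis (Abstract):** "Our hypothesis is that ZTE is concordant with CT for suture visualization and imaging diagnosis".
- **Target (section 1, Specific Aims):** "there will be 90% or greater concordance between ZTE and CT findings". The index, the unit of analysis and the treatment of direction are not defined.
- **Purpose (section 2, Background & Significance):** "If ZTE is shown to be non-inferior to CT for evaluation of craniosynostosis", clinical practice is expected to improve. No margin or test for this appears anywhere.
- **Data (section 3.4):** four readers rate "visibility of each major cranial suture and fontanelles [1 = poorly seen, 2 = partially seen, 3 = fully seen" on each modality. The scale is ordered, so direction is recorded.
- **Analysis (section 3.5):** "Interobserver agreement will be summarized by the kappa coefficient statistic and corresponding 95% confidence intervals". No other statistic is named. The section does not say whether kappa applies to visibility, diagnosis or both, and its sample size is framed on presence or absence of craniosynostosis.

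**The concern.** Visibility is a quality score: 3 is meant to be better than 1. To replace CT, one needs to know whether ZTE shows each suture and fontanelle about as well as CT does. Interobserver kappa involves only one modality at a time and does not depend on whether the shared score is high or low. ZTE-CT concordance involves both modalities but treats a gain and a loss alike. Carried out as written, the plan could report its kappa and its concordance and still leave open whether ZTE displays sutures as well as CT. That is half of the stated hypothesis.

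**Working it through.** **1. The plan's own figure.** Section 3.5 gives 37 patients for kappa above 0.7 when true kappa is 0.95, with 4 raters, alpha 0.05, 80% power and an 80/20 split. Take N = (z_alpha + z_beta)² / Σ[(P1 - P0)²/P0], where P0 and P1 are the distributions of the number of positive ratings among 4 raters under kappa 0.7 and 0.95 (beta-binomial, prevalence 0.20). The sum is 0.1695. With one-sided alpha, N = (1.645 + 0.842)² / 0.1695 = 36.5, so 37. The figure reproduces with a one-sided test and two outcome levels, although the text says "Using 4 raters and 3 levels of rating for their assessment". It is a sample size for reader agreement on diagnosis. It contains no ZTE-CT difference.

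**2. Interobserver kappa does not depend on level.** Constructed tables, 37 patients by 4 readers, kappa = (Po - Pe)/(1 - Pe):
- *Poor ZTE, readers agree.* All readers score 30 patients 1 and 7 patients 2 (mean 44/37 = 1.19). Po = 1, so kappa = 1.00. With two stray ratings, one in each direction, Po = 36/37 = 0.973, Pe = (30/37)² + (7/37)² = 0.693, and kappa = 0.280/0.307 = 0.91.
- *Near-perfect ZTE.* All 148 ratings are 3 except four 2s in four different patients (mean 2.97). Each of those patients has pairwise agreement 0.5, so Po = (33 + 4 × 0.5)/37 = 0.946. Pe = (144/148)² + (4/148)² = 0.947. Kappa = -0.0015/0.0526 = -0.03.
- *Simulation.* With true reader kappa set at 0.95 and ZTE scores half 1 and half 2 (never fully seen), mean estimated kappa is 0.95 and it exceeds 0.7 in every replicate. One third each of 1, 2 and 3 gives the same. The kappa is an input here, so this only illustrates that the score level does not enter.

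**3. Concordance is unsigned.** One structure, one score per patient and modality, 37 patients. All changes are assumed to be one level, between 2 and 3. The difference is d = (better - worse)/37, with SE = √[(b + c) - (b - c)²/37]/37, where b and c are the numbers better and worse.

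| ZTE against CT | Concordance | Difference in fully seen (95% CI) |
|---|---|---|
| better in 6, worse in 0 | 31/37 = 83.8% | +16 points (4 to 28) |
| better in 0, worse in 6 | 31/37 = 83.8% | -16 points (-28 to -4) |
| better in 0, worse in 3 | 34/37 = 91.9% | -8 points (-17 to 1) |

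For the first row, d = 6/37 = 0.162 and SE = √(6 - 36/37)/37 = 0.061. The first two rows are opposite results with the same concordance.

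**4. How far concordance limits a loss.** At 90%, at least 34 of 37 must agree (33/37 = 89.2% falls short). At most 3 patients can be worse, a loss in fully seen of at most 3/37 = 8.1 points. The poor ZTE of step 2 against a CT scored 3 throughout has 0% concordance.

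**5. Why the full scale is needed.** If CT is 2 and ZTE is 1 in every child, the difference in proportion fully seen is 0, while the mean score difference is -1.

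**6. Precision at 37 (illustration).** The documents give neither a margin nor an SD, so both are assumed. For a paired non-inferiority test of mean score, one-sided 0.025 and true difference 0, power = Φ(margin × √37/SD - 1.96):

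| SD of paired difference | Margin 0.25: power (N for 80%) | Margin 0.30: power (N for 80%) |
|---|---|---|
| 0.4 | 97% (21) | >99% (14) |
| 0.6 | 72% (46) | 86% (32) |
| 0.8 | 48% (81) | 63% (56) |

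**The case against.** A reader might infer that a ZTE on which everyone sees the sutures badly would pass the study. The documents do not support that for concordance: against a good CT such a ZTE fails outright, and it agrees only if CT is equally poor. The effect comes from interobserver kappa alone. There is also no visibility criterion to pass. The 0.7 is a planning value for agreement on craniosynostosis, and the 90% is set for findings.

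Nor can it be said that concordance would accept a ZTE clearly worse than CT. The 90% target caps the loss at 3 of 37, and the interval in that case includes zero (exact McNemar p = 0.25).

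Three further objections have weight:
- Section 1 speaks of equivalent information, and a two-sided criterion is coherent with that. But concordance still cannot say which way a shortfall went, and section 2 speaks of non-inferiority.
- Section 3.4 does not say how a fused suture is scored. If fusion lowers the score, a higher ZTE score could be a closed suture read as open. This stands and shapes the fix.
- Section 3.1 excludes scans of undiagnostic quality, which limits how poor an analysed ZTE can be. It does not rule out scores of 1 or 2 for individual sutures.

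Finally, the ordered scores are collected on both modalities, so nothing is lost if the analysis is amended.

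**Conclusion.** The gap is real and lies in the analysis, not in data collection. The named statistic does not compare ZTE with CT, and the hypothesised concordance compares them without direction. In the constructed cases, kappa is 1.00 for a poorly displayed ZTE and -0.03 for a near-perfect one, and 83.8% concordance describes both a 16-point gain and a 16-point loss. The rating patterns are illustrative, not predictions; 0.7 and 90% serve only as the nearest stated values; and the concordance examples take one score per patient for one structure. The missing visibility criterion is part of the defect. Agreement remains a reasonable measure for the diagnosis rating and for reader consistency.

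**What to change.** In section 3.5:
- Make the main visibility analysis the paired ZTE-minus-CT difference in mean score on the full 1-3 scale, for each suture and fontanelle and overall, averaged over the four readers. Take 95% CIs from a bootstrap that resamples patients, so that several structures and readers per child are not treated as independent.
- Support it with the cross-tabulation of better, same and worse, and with the difference in proportion fully seen. The cross-tabulation also shows cases poor on both modalities, which any difference scores as zero.
- Base the visualization conclusion on the lower confidence limit against a margin that the sponsor fixes and justifies before analysis.
- State how fused sutures are scored, and report open and fused sutures separately, since a higher ZTE score on a fused suture may not mean better visualization.
- Keep interobserver kappa and ZTE-CT concordance for visibility as secondary descriptions.

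The cost is a short addition to 3.5, a scoring note in 3.4 and the work of justifying a margin. No extra patients, scans or reads are needed for the analysis itself. The downside is that the visibility claim becomes directional and may be inconclusive at 37 patients: across the assumed margins and SDs above, power runs from 48% to over 99%.

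### Equivalence to CT is judged by a fixed 90% concordance and a fixed kappa of 0.7, and neither is compared with how often CT reads agree with each other

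*Combined protocol and SAP*

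**What the plan says.** - **Aim (section 1, Specific Aims):** "To establish whether ZTE imaging of the infant calvarium can provide equivalent information to CT". The support offered is "This aim is based on the hypothesis that there will be 90% or greater concordance between ZTE and CT findings".
- **Background (section 2):** the hoped-for change in practice is conditional: "If ZTE is shown to be non-inferior to CT for evaluation of craniosynostosis". No margin is given there or elsewhere.
- **Sample size (section 3.5):** "we will have 80% power to claim the interobserver kappa statistics is greater than 0.7 when the true kappa is 0.95", "with type I error (alpha) fixed at 0.05" and an "expected 80/20 probability of the absence or presence of craniosynostosis, respectively", with four raters, three rating levels and 37 patients. The section does not say whether the kappa refers to CT, ZTE or both.
- **Analysis (section 3.5):** interobserver kappa with 95% confidence intervals, and nothing else. No estimator, unit or success criterion is given for the 90%.
- **Reads (sections 3.3 and 3.4):** four neuroradiologists each read both modalities. The diagnosis is rated present, absent or unable to tell.

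**The concern.** A claim of equivalence or non-inferiority asks whether replacing a CT read by a ZTE read adds disagreement beyond what two CT reads already show. Neither yardstick answers that. The 90% is absolute, with no stated rationale and no CT-CT reference. The kappa measures agreement among readers: four readers can agree almost perfectly on a ZTE image that contradicts the CT of the same child.

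The meaning of 90% therefore depends on a quantity the plan never sets beside it. If CT reading is precise, 90% is lenient. If CT reading is noisy, 90% is strict, and a true equivalent may miss it. The stated purpose is to replace CT in children being considered for skull surgery, so what the result can support matters. Defining and computing a ZTE-CT concordance would not cure this, because the threshold would still have no CT reference.

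**Working it through.** **Inputs.** From section 3.5: 80/20 split, expected kappa 0.95, kappa to exceed 0.7, four raters, 37 patients, alpha 0.05, power 80%. From section 1: 90% concordance. Assumed: the share rated unable to tell, and (for the simulation) a model of how ZTE might differ from CT.

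**The plan's own figure.** A one-degree-of-freedom goodness-of-fit sample size for kappa is N = (z_alpha + z_power)² / Σ[(P_i(0.95) − P_i(0.7))² / P_i(0.7)], where P_i is the distribution of positive calls among four raters. With a beta-binomial model at prevalence 0.2 and one-sided alpha 0.05, the sum is 0.1695 and N = (1.645 + 0.842)² / 0.1695 = 36.5, so 37. The stated size reproduces under this variant (two-sided gives 46.3; the plan does not state sidedness). It concerns reader kappa only. Nothing below depends on it except through the number of patients.

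**Reader disagreement implied by the plan, two levels.**
- Chance agreement: 0.8² + 0.2² = 0.68, so chance disagreement is 0.32.
- Kappa 0.95: 0.05 × 0.32 = 1.6% disagreement (98.4% agreement).
- Kappa 0.70: 0.30 × 0.32 = 9.6% disagreement (90.4% agreement).
- 90% concordance allows 10%: 10/1.6 = 6.25 times the first figure, 10/9.6 = 1.04 times the second.

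**Three levels.** Let u be the share unable to tell, with the rest split 80/20. At kappa 0.95, disagreement is 0.05 × (1 − Σp²). For u = 20%: Σp² = 0.64² + 0.16² + 0.20² = 0.4752, disagreement is 2.6%, and the ratio is 3.8.

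| u (assumed) | 0% | 2% | 5% | 10% | 20% |
|---|---|---|---|---|---|
| 10% ÷ reader disagreement at kappa 0.95 | 6.25 | 5.8 | 5.2 | 4.6 | 3.8 |

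**Can reader kappa be high while ZTE contradicts CT?** Simulation: 37 patients, four readers, two levels, 20% truly positive, reader error set to give kappa 0.95 on CT, and ZTE showing the opposite of CT in a fraction q of children. For illustration, 90% counts as reached when the pooled same-reader point estimate is at least 90%. That is an assumption, not a rule in the plan.

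| q | Expected CT-ZTE concordance | ZTE reader kappa | Trials reaching 90% |
|---|---|---|---|
| 8.7% (about 3 of 37) | 90.0% | about 0.96 | about 53% |
| 4.3% | 94.2% | about 0.95 | about 88% |

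In the other direction, with q = 0 and reader kappa 0.70 on both modalities, a perfect substitute agrees with CT about 89% of the time and reaches 90% in fewer than four trials in ten (39% in one run).

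**How a formal rule based on the difference would behave at this size.** Take CT-ZTE agreement across different readers minus CT-CT agreement, require the lower limit of a percentile bootstrap 95% interval to lie above −5 points (an illustrative margin), and use the same model.
- Interchangeable ZTE: passes 98% at reader kappa 0.95, about 78% at 0.85 and about 53% at 0.70.
- True difference −5 points, reader kappa 0.95: passes about 14%, against a nominal 2.5%. The reason is sparse data. A −5 point difference needs q = 0.05/(1 − 2 × 0.016) = 0.0517, and the chance that none of 37 children is contradicted is 0.9483³⁷ = 0.14. A bootstrap of such a sample cannot show the deficit.

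**The case against.** The strongest reply is that 90% is a hypothesis in the aims and no decision rule hangs on it. That stands. A reader might infer that the plan would declare ZTE equivalent at an observed 90%. The documents do not say so, and the percentages of trials reaching 90% show only what such a reading would imply.

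A reader might also take the factor of six as a property of CT. It is not. The 0.95 is a planning value for an unspecified modality, the 6.25 uses two levels where the scale has three, and it compares a minimum with an optimistic expectation. Against the plan's own floor of 0.70 the ratio is about 1. This limits the headline figure, but it also shows that 90% can be lenient or strict depending on CT-CT agreement.

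It is tempting to say that the two yardsticks contradict each other, because 90% agreement is kappa (0.90 − 0.68)/0.32 = 0.69, below 0.70. The gap is only 0.4 points of agreement (90.0% against 90.4%), and the two measure different things. No inconsistency follows.

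Nor is a fixed agreement target against a reference modality invalid in itself, if its rationale and limits are stated; here neither is. Finally, a pass/fail rule on the difference is no clean replacement. As shown above, it passes too often at the margin and can fail a true equivalent when reading is noisy. That argues for estimating the difference, not for leaving it out.

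**Conclusion.** The concern holds in a limited form. The aim and background make claims relative to CT, while both yardsticks are absolute and the planned analysis is of reader agreement only. On the plan's figures, 90% concordance tolerates roughly four to six times the reader disagreement expected at kappa 0.95 (unable-to-tell share 0% to 20%), and about the same disagreement as kappa 0.70. Reaching 90% therefore does not by itself show equivalence, and missing it does not refute it. High interobserver kappa is compatible with ZTE contradicting CT in several children.

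This rests on the 80/20 split applying to the diagnosis ratings, on the planning kappa standing in for CT-CT agreement, and, for the simulated figures, on the two-level model. It does not show that the plan contains a faulty equivalence test, since it contains none. It should be fixed, because the remedy costs little and changes what the trial can conclude, but it does not invalidate the study.

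**What to change.** In section 3.5, using only the reads already planned:

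1. Estimate CT-CT agreement on diagnosis over the 6 reader pairs.
2. Estimate CT-ZTE agreement over the 12 pairings of different readers (4 × 3). Different readers keep it comparable with step 1, which is also between readers.
3. Report step 2 minus step 1 with a 95% interval that treats the patient as the unit, and report the share rated unable to tell on each modality.
4. Report the paired ZTE-minus-CT difference in interobserver kappa beside the kappa result.
5. Base any wording about equivalence or non-inferiority on the difference and its interval. Keep 90% as a descriptive benchmark.

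If the sponsor wants a formal non-inferiority claim, it should fix and justify a margin before any read and use an interval method checked at this sample size. The percentile bootstrap should not be adopted unchecked.

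Cost: about a paragraph and a few hours of analysis, with no new patients, scans or reads. Downside: 37 patients were sized only for kappa, so the interval may be wide and the claim in section 1 may have to be softened.

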3.1 Study population/Patient Enrollment

Eligibility criteria - Inclusion:

Pediatric patients 0-18 of age will be recruited by our surgical colleagues based on the clinical concern for craniosynostosis and possible need for calvarial reconstruction. Study Team will also review the surgical calendars and Mayo Clinic data base (MDE, i2b2) searching for potential pediatric patients. When a patient is found they will email the surgeons for a review and verification of qualification for the study. Patients must have gotten a clinically indicated CT within a 6 week time period from the ZTE MRI.

Eligibility criteria - Exclusion:

Exclusion criteria include lack of consent, clinical CT scan of the head, contraindication/inability to undergo both examinations within the designated time period and/or undiagnostic image quality. Pregnancy (women of childbearing age will be given a urine pregnancy test).

Patients will undergo ZTE within a 6 week time period from the CT scan (though attempting with each patient to schedule on the same day). ZTE MRI examinations will be added, when possible, to a patient's already scheduled MRI or will take place as a standalone appointment without sedation.

Patient preparation

A Review Preparatory to Research will be conducted by the study coordinators to determine if the patient meets inclusion criteria including a pre-screen for MRI safety.

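### The 90% ZTE-CT concordance hypothesis is undefined and has no planned analysis: section 3.5 covers only agreement between readers, which cannot show misses that all readers share

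*Combined protocol and SAP*

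**What the plan says.** Specific Aims sets out to learn whether ZTE can "allow for a reliable diagnosis of craniosynostosis in a child" and rests this on the hypothesis that "there will be 90% or greater concordance between ZTE and CT findings". The Abstract names two targets and a consequence: "ZTE is concordant with CT for suture visualization and imaging diagnosis, permitting its use in the clinical setting".

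Sections 3.3 and 3.4 have four neuroradiologists read both CT and ZTE. Each gives a three-level suture visibility score and a three-level score for "confirmation of diagnosis based on the clinical question" (present, unable to tell, absent). Paired ZTE and CT ratings will therefore exist for every reader and patient.

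Section 3.5 sizes the study at 37 patients to show interobserver kappa above 0.7 when the true value is 0.95, using an "expected 80/20 probability of the absence or presence of craniosynostosis, respectively". Its only planned summary is: "Interobserver agreement will be summarized by the kappa coefficient statistic and corresponding 95% confidence intervals". It does not say whether kappa is computed per modality.

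Under section 3.1, surgeons recruit children on "clinical concern for craniosynostosis and possible need for calvarial reconstruction", and "undiagnostic image quality" is an exclusion with no modality named.

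**The concern.** The hypothesis concerns ZTE against CT; the planned statistic concerns reader against reader. Someone who followed section 3.5 exactly would finish without testing the hypothesis in Specific Aims. The two quantities can also diverge. If ZTE fails to display a fused suture, all four readers may call it absent, and they then agree perfectly with each other while disagreeing with CT.

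The 90% figure could be computed after the fact, but the documents do not fix its unit (patient, suture or read), how four readers are combined, how an unable-to-tell score counts, or whether the estimate or a confidence limit must reach 90%. A single overall agreement figure also hides which kind of disagreement occurred. If ZTE is to spare children a CT, a missed CT-positive is a different error from a false alarm.

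**Working it through.** **The plan's own figure.** A goodness-of-fit sample size under the common-correlation model (4 raters, kappa 0.95 against 0.70, 80% power) gives 51 patients two-sided or 41 one-sided if 80/20 is read as two levels. It gives 38 for an assumed three-level split of 70/20/10 two-sided or 78/20/2 one-sided. Section 3.5 states neither the third-level share nor the sidedness, so 37 can be neither confirmed nor refuted. Below, 37 is used only as the planned size.

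**Inputs.** n = 37, four readers and 20% presence (section 3.5); 90% (Specific Aims). Assumptions: one two-category call per patient, all 37 evaluable, and 90% read as a point estimate.

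**How many disagreements pass.** 34/37 = 91.9% meets 90%; 33/37 = 89.2% does not. So at most 3 discordant patients.

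**CT-positives.** 0.20 × 37 = 7.4, so 7 or 8. A ZTE read as negative in every child would already agree with CT in 30/37 = 81% or 29/37 = 78%.

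**Worst case at 20% prevalence: all 3 are misses (Clopper-Pearson intervals).**
- 7 positives: sensitivity 4/7 = 57% (95% CI 18-90%).
- 8 positives: sensitivity 5/8 = 63% (95% CI 24-91%).
- Large-sample bound with specificity 1: (0.90 − 0.80)/0.20 = 50%.

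**What kappa shows.** ZTE-CT Cohen kappa, from both positive / missed / false positive / both negative:
- 4, 3, 0, 30: observed agreement 0.919, chance agreement 0.744, kappa (0.919 − 0.744)/(1 − 0.744) = 0.68.
- 5, 3, 0, 29: kappa 0.72.

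If all four readers miss the same 3 children and agree elsewhere, the interobserver (Fleiss) kappa on ZTE is 1.0.

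**Pooling 37 × 4 = 148 reads instead.** 134/148 = 90.5% passes and 133/148 = 89.9% fails, so 14 missed reads are allowed: sensitivity 14/28 = 50% or 18/32 = 56%.
- Misses concentrated (3 patients missed by all readers, 1 by two): Fleiss kappa 0.89 with 7 positives, 0.92 with 8.
- Misses scattered (two readers in each of 7 patients): Fleiss kappa 0.26.

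**Other prevalences, 3 discordant patients.**

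| CT-positive share | Sensitivity if all 3 are misses | Specificity if all 3 are false positives |
|---|---|---|
| 20% | 4/7 to 5/8 = 57-63% | 26/29 to 27/30 = about 90% |
| 50% | 15/18 to 16/19 = 83-84% | 15/18 to 16/19 = 83-84% |
| 80% | 26/29 to 27/30 = about 90% | 4/7 to 5/8 = 57-63% |

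**If a limit must reach 90%.** The exact 95% lower limit is 90.5% for 37/37 and 85.8% for 36/37, so only complete agreement passes and no miss is allowed.

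**What the stratum can show.** Perfect detection has an exact lower limit of 59% (7/7) or 63% (8/8). A lower limit above 90% needs 36/36 (90.3%); 35/35 falls just short (89.997%).

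**The case against.** The strongest reply is that 57-63% is an extreme. It needs a point-estimate reading of 90%, exactly 3 discordant patients, and all 3 on the same side. Were 3 disagreements scattered at random over 37 patients, all would be CT-positive with probability 0.45% (7 positives) or 0.72% (8). That stands as a caution: the figure is what the criterion would let pass, not a forecast. Random scatter is not the natural model either, since misses caused by the image would be directional.

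The 20% is a planning input for kappa, and surgical referral may bring a higher share of CT-positives. This also stands; the table shows the sensitivity problem shrinking as the specificity problem grows, which is the reason to report both strata.

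Three stronger readings are tempting but unsupported.
- That the planned kappa could never reveal poor ZTE detection: it drops to 0.26 when misses are scattered and is blind only to those that all or most readers share.
- That the study is a non-inferiority trial lacking a margin: the term appears only in a conditional sentence of Background & Significance, not as an objective or test.
- That 34/37 would license clinical use: the Abstract links concordance to clinical use, but no decision rule says so.

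Finally, with 7-8 positives any sensitivity estimate will be imprecise. True, but that argues for showing the interval.

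**Conclusion.** The concern holds in a limited form. The gap itself needs no arithmetic: the concordance hypothesis has no operational definition and no planned analysis, and interobserver kappa cannot stand in for one because shared misses leave it unchanged.

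The size is conditional. On a patient-level point-estimate reading of the diagnosis rating, with 37 evaluable patients and 20% CT-positive, 90% agreement is compatible at worst with a sensitivity of 57-63%. Under a lower-limit reading that example disappears. A reader might infer that ZTE is expected to miss about 40% of cases, or that the sample size is wrong; the documents support neither. The change is worth making because the claim at stake is clinical use and the data will already be in hand.

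**What to change.** In Specific Aims and section 3.5:

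1. Define ZTE-CT concordance for the diagnosis rating: the unit, how the four readers are combined, and the handling of unable-to-tell on ZTE (counted as non-agreement, or shown both ways). State whether the point estimate or a confidence limit must reach 90%, and whether the 90% also applies to suture visibility.
2. Add a ZTE-CT agreement analysis from the paired ratings, overall and separately in CT-positive and CT-negative patients. Set CT status by a pre-stated rule, for example the majority of the four CT reads, with ties and uncertain majorities reported separately. Give 95% CIs that allow for four readers per patient (for example a patient-level bootstrap), plus an exact CI on the majority call, because the bootstrap collapses when all reads agree.
3. Report exclusions for undiagnostic images by modality; otherwise failed ZTE scans can leave the data before agreement is computed.
4. Base any diagnostic claim on both strata. State that with 7-8 CT-positives even perfect detection has an exact lower limit of only 59-63%, so sensitivity is an estimate and not proof that ZTE can replace CT.

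The planned kappa stays. Cost: protocol wording, a count of exclusions and a short extra analysis, with no new patients or reads. The downside is a visibly wide sensitivity interval and a more modest conclusion.
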